## 8.2.9 Cervical cytology

- Cervical smear will only be performed before randomization to ensure eligibility and is not a safety endpoint.
- Cervical smear will be performed only if the participant has an intact cervix.
- Cervical smear performed during the last 12 months prior to signing of informed consent can be used for the screening assessment.
- Participants with ASCUS are eligible for the study if they have negative result for high-risk HPV strains from an HPV deoxyribonucleic acid test.
- Cervical smear can be repeated once in case of insufficient material in the sample.
- If cervical smear and endometrial biopsy are scheduled for the same day, cervical smear should be conducted first.

## 8.2.10 Endometrial biopsy

### Timing and sampling of endometrial biopsy

- Endometrial biopsy is to be performed only when applicable (i.e. women with intact uterus) at time points indicated in the SoA. All endometrial biopsies must be collected by qualified personnel.
- Each participant should have an endometrial biopsy with a normal result (disordered proliferative endometrium, hyperplasia, polyp, and malignant findings will be considered as abnormal) documented at screening.
- If postmenopausal status has not been confirmed prior to the endometrial biopsy, a urine pregnancy test and a transvaginal ultrasound must be performed before conducting the biopsy.
- If a cervical smear sample is collected at the same visit, it must be performed before performing the biopsy.
- Unscheduled biopsy should be performed in case of an abnormal finding in the TVU and/or if the participant has experienced post-menopausal bleeding during the study.
- The sterilized, disposable device Pipelle de Cornier will be used – a flexible and transparent polypropylene sheath with an internal plunger for aspiration. This device allows for gentle tissue sampling, without hysteroscopy, and generally requires no local anesthesia or cervical dilatation.
- If necessary for pain prophylaxis or relief relating to the endometrial biopsy procedure, the use of an analgesic is permitted and will be documented as concomitant medication.

### Assessment of endometrial biopsies

All biopsy samples will be processed via the central laboratory and will be evaluated independently by three pathologists who are blinded with regard to treatment assignment.

If the baseline biopsy is interpreted by at least one of the reviewing pathologists to contain findings that constitute an exclusion criterion, the participant must be excluded from the study. Details can be found in the Operational Manual for Pathology Reads.

Study sites will be informed about the individual diagnoses of the three pathologists to allow for clinical follow-up.

In case a sample is considered “not evaluable” by two or more of the pathologists, a repeat sample will be requested by the central laboratory.

- At screening, an evaluable sample is required for inclusion. Women with a diagnosis of disordered proliferative endometrium, endometrial hyperplasia, polyp, or malignant neoplasm by any of the three pathologists will not be included.
- At end-of-treatment, the requirement for a repeat biopsy after a non-evaluable sample is at the discretion of the investigator. The decision should take into account endometrial thickness and clinical findings.

### **8.2.11 Sleepiness Scale**

The sleepiness scale is a Sponsor developed questionnaire containing 3 items assessing the degree of sleepiness experienced by the participant in the morning, in the afternoon and in the evening of the same day. The Sleepiness Scale will be assessed together with the HFDD evening diary at bedtime during selected time periods, using the electronic hand-held device. In case one entry on the Sleepiness Scale was missed, retrospective data entry is possible for a pre-defined period of time (see Section 8.1.1, subsection “Measures to further prevent missing participants’ hand-held device entries”).

Participants respond to the items using a 5-point verbal rating scale (“0”=not at all; “4”=very much). For the assessment of sleepiness 7-day averages of daily individual single item scores and 7-day averages of an aggregated overall sleepiness score will be used.

During the screening period assessments will be done daily in the evenings together with the HFDD assessment. During the treatment period the assessment will be done on 7 consecutive evenings at timepoints indicated in the SoA.

### **8.2.12 Suicidal ideation and behavior: Electronic Columbia-Suicide Severity Rating Scale (eC-SSRS)**

Suicidal ideation and behavior will be monitored by eC-SSRS questionnaire. Use of the eC-SSRS is required by the US FDA in clinical trials of new compounds with a central mode of action.

The eC-SSRS is a fully structured participant rated questionnaire designed and developed for computer administration. Participants respond to standardized clinical questions presented in a uniform fashion and adhering to the original C-SSRS clinical conventions. The eC-SSRS assesses lifetime suicidality during an initial baseline evaluation, and then prospectively monitors ideations and behaviors at subsequent follow-up assessments. The eC-SSRS assesses the severity and frequency of suicidal ideation and behavior. The information collected in the eC-SSRS is classified into a set of 11 categories for suicidal ideation and suicidal behavior, and self-injurious behavior without suicidal intent.

See Exclusion Criteria 16 for information on when the participant should not be randomized based on suicidal behavior or ideation.

The investigator will receive an email notification if a participant has a “Yes” score on item 4 or item 5 of the suicidal ideation section of the eC-SSRS or “Yes” on any item of the suicidal behavior section. If this happens after randomization, the participant can continue the study at the discretion of the investigator. The investigator has to report this as an adverse event. In addition, any suicidal ideation and/or behavior should be treated according to local clinical practice.

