### Other Exclusions

16. At screening a suicidal ideation in the past 6 months (as indicated by "Yes" on item 4 or item 5 of the suicidal ideation section of the eC-SSRS) or suicidal behavior in the past 6 months (indicated by "Yes" on any item of the suicidal behavior section of the eC-SSRS).
17. Clinically relevant drug or alcohol abuse within 12 months of signing of informed consent.
18. Dependent on the investigator, the contract research organisation(s) or Sponsor for education or employment (e.g. family members, employees, people who receive grants/education).
19. Known hypersensitivity to elinzanetant or any of the excipients in the formulation.
20. Inability to comply with the study procedures for any reason, including the following examples: language comprehension, psychiatric illness, general inability to get to the study site.

---

 Clinically relevant alcohol or drug abuse is behavior that meets the DSM-5 criteria for substance use disorder (DSM-5:Diagnostic and Statistical Manual of Mental Disorders).

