**Table 1–1: Objectives and endpoints**

Objectives	Endpoints
Primary 

• To evaluate the efficacy of elinzanetant for the treatment of VMS associated with the menopause

	Primary endpoint Mean change in frequency of moderate to severe HFs from baseline to Week 12 (assessed by HFDD)  Exploratory endpoints 

• Mean change in frequency of moderate to severe HF from baseline over time (assessed by HFDD)

• Mean change in severity of moderate to severe HF from baseline over time (assessed by HFDD)

• Mean change in frequency of mild, moderate, and severe HF from baseline over time (assessed by HFDD)*

Objectives	Endpoints
Secondary	

 
To evaluate the efficacy of elinzanetant on: 
 
sleep quality
 
menopause related quality of life
 
weight and body composition
 
 
 
 
in women being treated for relief of VMS associated with the menopause
	
Secondary endpoints:
 
 
Mean change in PROMIS SD SF 8b total score from baseline over time
 
Mean change in MENQOL total score from baseline over time
 
 
Exploratory endpoints:
 
 
Mean change in MENQOL domain and single item scores from baseline over time*
 
Mean change in body weight from baseline over time
 
Mean change in body composition from baseline over time
 
Mean change in frequency of nighttime awakening from baseline over time (assessed by HFDD)*
 
Mean change in proportion of days with participant rating of “quite a bit” or “very much” sleep disturbance due to HFs from baseline over time (assessed by HFDD)*
 

 
To evaluate the safety of elinzanetant for the treatment of VMS associated with the menopause
 
	
Other endpoints:
 
 
Number of participants with non-benign endometrial biopsy results
 
Mean percentage change in BMD from baseline to Week 52
 
Number of participants with TEAEs
 
Number of participants with abnormal laboratory parameters
 
Mean change in sleepiness score assessed by Sleepiness Scale at Week 1, Week 4, Week 12, Week 24, Week 36, Week 50 compared to baseline.
 

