### 5.6.2 Adverse Events

Adverse events (AEs) will be collected from the start of study intervention until the last follow-up. (Serious) Adverse events ((S)AEs) which are related to protocol required study procedures (e.g., (S)AE related to invasive study procedures) will be recorded as (S)AEs from the signing of the ICF (pre-treatment (S)AEs). Any medical occurrences/conditions that begin

in the period between signing Informed consent form (ICF) and the start of study intervention, and which are not related to a protocol-required study procedure, will be recorded on the Medical History/Current Medical Conditions, not as AEs.

All AEs will be summarized by treatment group using the Medical Dictionary for Regulatory Activities (MedDRA) preferred terms (PT) grouped by system organ class (SOC) (the current version at the time of analysis) and classified into pre-treatment, treatment-emergent (TEAE) and post-treatment AEs. Incidences of TEAEs and TESAEs per 100 person-years will be summarized by treatment group. The rate per 100 person-years is calculated as

Rate per 100 person-years = number of subjects / (total drug exposure in years / 100),  
where 365.25 days are taken as one year.

A TEAE is defined as any adverse event occurring or worsening on or after the date of the first dose of study drug up to 14 days after the date of the last dose of study drug. AEs will be flagged as TEAE except for AEs for which there is clear evidence that the AE starts before date of first study drug intake (pre-treatment AEs) or after the date of last study drug intake + 14 days (post-treatment AEs).

If the severity of a previously reported event worsens or if the relationship to study intervention/protocol required procedures changes, two separate events should be reported.

Worsening of an AE is defined as follows:

- AE intensity is worsened (e.g., moderate to severe)
- AE changed to a serious event
- AE ends with death

In case an AE starts before the date of last study drug intake + 14 days and worsens after last study drug intake + 14 days will be considered as two AEs, a TEAE and a post-treatment AE.

Partially missing onset AE date will be imputed following a worst-case approach as described in section [5.1.1](#).

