### **5.6.3.12 Electronic Columbia-Suicide Severity Rating Scale (eC-SSRS)**

Suicidal ideation and behavior will be monitored by eC-SSRS questionnaire. The eC-SSRS assesses lifetime suicidality during an initial baseline evaluation, and then prospectively monitors ideations and behaviors at subsequent follow-up assessments. The eC-SSRS assesses the severity and frequency of suicidal ideation and behavior.

eC-SSRS outcomes will be summarized by treatment group and by visit using descriptive statistics for continuous variables and frequency tables for categorical outcomes as described in Section 5.1.

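### The SAP tabulates the eC-SSRS only by arm and visit, so it specifies no per-woman summary of any, worst, or new-or-worse suicidal ideation or behaviour after baseline

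*Protocol*

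**What the plan says.** Protocol 8.2.12 includes the scale because the US regulator requires it for new compounds acting centrally. Answers fall into 11 categories covering suicidal ideation, suicidal behaviour, and self-injury without suicidal intent. The recall periods differ: "The eC-SSRS assesses lifetime suicidality during an initial baseline evaluation, and then prospectively monitors ideations and behaviors at subsequent follow-up assessments". Protocol Table 1-1 places the first administration at SCR-2.

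The analysis is a single sentence in SAP 5.6.3.12: "eC-SSRS outcomes will be summarized by treatment group and by visit using descriptive statistics for continuous variables and frequency tables for categorical outcomes".

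Four other provisions bear on the point:

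- **Adverse-event trigger (Protocol 8.2.12).** After randomization, a positive answer on ideation item 4 or 5, or on any behaviour item, has a consequence: "The investigator has to report this as an adverse event".
- **Adverse-event tables (SAP 5.6.2).** Events are tabulated by arm and by preferred term within system organ class, and classed as pre-treatment, treatment-emergent or post-treatment. A TEAE is one "occurring or worsening on or after the date of the first dose of study drug up to 14 days after the date of the last" intake. SAP Table 1-1 lists "Number of participants with TEAEs" as an endpoint.
- **Eligibility (Protocol 5.2, exclusion 16).** The criterion begins "At screening a suicidal ideation in the past 6 months" and applies to items 4 and 5. Suicidal behaviour in the same window also excludes.
- **Unscheduled assessments (SAP 5.1.2).** By default these are listed and left out of summary tables.

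**The concern.** For a rare safety outcome the useful quantity is the number of women in each arm who had the event at any time after baseline, how bad it was at its worst, and whether it was new or worse for that woman. A by-visit table answers a different question, namely how many women were positive on a given form. Repeat reports by one woman and single reports by several women look the same in it.

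The baseline column adds a second difficulty. It covers a lifetime, while each later column covers only prospective monitoring. A fall after baseline is therefore expected in both arms without any real change, and the SAP gives no rule for comparing the two kinds of answer.

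The SAP does specify participant-level summaries elsewhere. SAP 5.6.3.4.1 counts participants by post-baseline liver category, allows unscheduled values, and plots each woman's maximum post-baseline value. SAP 5.6.3.8 lists women with at least one scan beyond a threshold. The eC-SSRS has nothing comparable.

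**Working it through.** The documents state no eC-SSRS rate, power or precision, so there is no figure of the plan's own to reproduce. The check is a count of administrations, a comparison of the two counting routes, and an illustration.

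**1. Post-baseline administrations.** The eC-SSRS row of Protocol Table 1-2 is marked at T1, T2, T3, T4, T5, T7, T9/EoT and FU. That is 8: seven in the treatment period or at end of treatment, and one at follow-up.

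**2. What visit counts reveal about women.** Let c(v) be the number positive at visit v in one arm. The number of women ever positive lies between the largest c(v) and the sum of all c(v). With one positive at each of 8 visits, the range is 1 to 8 women. On 300 women that is 1/300 = 0.3% to 8/300 = 2.7%, and the planned tables cannot say where in that range the truth lies.

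**3. What each route counts.**

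| Report after baseline | eC-SSRS tables (SAP 5.6.3.12) | AE route (Protocol 8.2.12, SAP 5.6.2) |
|---|---|---|
| Ideation items 1–3 | by visit only | no mandatory report |
| Ideation item 4 or 5 | by visit only | per woman, by preferred term |
| Suicidal behaviour | by visit only | per woman, by preferred term |
| Worst category per woman | none | none |
| Shift from eC-SSRS baseline | none | none |

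Suicidality is not among the AESIs in SAP 5.6.2 and has no grouped search in SAP 6.7. Ideation and behaviour may therefore sit under different preferred terms with no combined row. Worsening in SAP 5.6.2 means higher AE intensity, a change to serious, or death. It does not mean movement from the woman's eC-SSRS baseline.

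**4. Illustration.** Arm size n = 300 (SAP 3). The proportion p ever positive is assumed. Women ever positive = n × p. If each is positive once and reports spread evenly, the count per visit = n × p / 8.

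| Assumed p | Women per arm | Per visit table |
|---|---|---|
| 0.5% | 1.5 | 0.19 |
| 1% | 3 | 0.38 |
| 2% | 6 | 0.75 |
| 3% | 9 | 1.12 |

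A split of 6 v 0 women out of 300 per arm gives a two-sided Fisher p of 0.03. A split of 1 v 0 at a single visit gives p = 1.0. For 9 v 3 women the difference is 9/300 − 3/300 = 2.0 percentage points, with a Newcombe 95% interval of −0.4 to 4.7.

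**The case against.** The strongest reply is that the events that matter most are already counted across visits. Item 4/5 ideation and any suicidal behaviour must be reported as AEs, and the TEAE tables count participants. Exclusion 16 keeps out women with such reports in the six months before screening, so for these events a positive after randomization is already new against that window. This stands. A reader might infer that nothing in the plan counts women with new suicidal ideation or behaviour; the documents do not support that. What remains uncovered is items 1 to 3, a combined row across preferred terms, and any comparison with lifetime history.

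A reader might also infer that late-visit denominators shrink to the roughly 210 women in SAP 3. That figure is women in the elinzanetant arm treated for one year, not women assessed. Protocol 7.1 asks those who stop treatment to stay until T9 with scheduled procedures continuing, and Table 1-2, footnote a, gives them an end-of-treatment visit with the Week 52 assessments. The figure does not measure loss of eC-SSRS data.

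Other replies have some force:

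- If every scheduled cell is zero, the per-woman count from scheduled visits is also zero. The gap matters only when there are positives, or when one arises at an unscheduled assessment.
- The recall difference affects both arms alike, so it does not bias the comparison between arms. It spoils only the reading from baseline to later visits.
- All safety analyses are descriptive (Protocol 9.4.5), the eC-SSRS is not a listed endpoint, and a DSMB receives unblinded safety data. These points limit the weight of the gap without closing it.
- SAP 1 places table specifications in a separate document, so an across-visit table may exist there. If it does, the SAP needs only a sentence to specify it.

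**Conclusion.** The point holds as a gap in the specified safety reporting. SAP 5.6.3.12 defines no participant-level summary of any, worst, or new-or-worse post-baseline ideation or behaviour, and the planned visit tables cannot be turned into one. The AE route covers the most severe answers only, indirectly and by separate terms. Ideation items 1 to 3 would be counted per woman only if an investigator chose to report them.

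The size depends on an event rate that the documents do not give. Over an assumed 0.5% to 3%, 1.5 to 9 women per arm would be spread over eight tables at about 0.2 to 1.1 each. That rests on 300 women per arm, one positive report per woman and even spread. Even a per-woman table would describe a small signal rather than settle it: the interval for 9 v 3 includes zero. The primary efficacy result is not affected.

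**What to change.** In SAP 5.6.3.12, before unblinding, add one table on the SAF, by arm, with the number and percentage of women who had:

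- any post-baseline suicidal ideation, classified by the worst of the five levels;
- any suicidal behaviour;
- self-injury without suicidal intent.

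State that unscheduled assessments count, since the default rule would exclude them. Show reports from first dose to last dose + 14 days, allocated by assessment date, separately from later off-treatment and follow-up reports. The first window matches the TEAE definition. The second is needed because the follow-up visit comes about four weeks after treatment, and women who stop drug early may be assessed until T9. A report whose recall crosses the cutoff goes by its assessment date; with both parts shown, none is lost.

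Add a shift from the worst baseline category to the worst post-baseline category, naming the baseline window: lifetime, and past six months where recorded. Keep the by-visit table.

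The cost is SAP wording and one extra descriptive table from data already collected. No assessment or visit changes.

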### **8.3 Adverse Events (AEs), Serious Adverse Events (SAEs) and Other Safety Reporting**

The definitions of adverse events (AEs) and serious adverse events (SAEs) can be found in Section [10.3](#).

AEs will be reported by the participant (or, when appropriate, by a caregiver, surrogate, or the participant's legally authorized representative).

The investigator and any qualified designees are responsible for detecting, documenting, and recording events that meet the definition of an AE or SAE and remain responsible for following up all AEs (see Section [7](#)).

The method of recording, evaluating, and assessing causality of AEs and SAEs and the procedures for completing and transmitting SAE reports are provided in Section [10.3](#).

#### **8.3.1 Time Period and Frequency for Collecting AE and SAE Information**

(S)AEs will be collected from the start of study intervention until the last follow-up visit at the time points specified in the SoA (Section [1.3](#)). (S)AEs which are related to protocol-required study procedures (eg, (S)AE related to invasive study procedures) will be recorded as (S)AEs from the signing of the ICF.

Any medical occurrences/conditions that begin in the period between signing ICF and the start of study intervention, and which are not related to a protocol-required study procedure, will be recorded on the Medical History/Current Medical Conditions, not as AEs.

All SAEs will be recorded and reported to the sponsor or designee immediately and under no circumstance should this exceed 24 hours of learning of the event, as indicated in Section [10.3](#). The investigator will submit any updated SAE data to the sponsor within 24 hours of it being available.

Investigators are not obligated to actively seek information on AEs or SAEs after conclusion of the study participation. However, if the investigator learns of any SAE, including a death, at any time after a participant has been discharged from the study, and he/she considers the event to be reasonably related to the study intervention or study participation, the investigator must promptly notify the sponsor.

### **8.3.2 Method of Detecting AEs and SAEs**

Care will be taken not to introduce bias when detecting AEs and/or SAEs. Open-ended and non-leading verbal questioning of the participant is the preferred method to inquire about AE occurrences.

### **8.3.3 Follow-up of AEs and SAEs**

After the initial AE/SAE report, the investigator is required to proactively follow each participant at subsequent visits/contacts. All SAEs, and AEs of special interest (as defined in Section 8.3.6), will be followed until resolution, stabilization, the event is otherwise explained, or the participant is lost to follow-up (as defined in Section 7.3). Further information on follow-up procedures is provided in Section 10.3.

### **8.3.4 Regulatory Reporting Requirements for SAEs**

- Prompt notification by the investigator to the sponsor of an SAE is essential so that legal obligations and ethical responsibilities towards the safety of participants and the safety of a study intervention under clinical investigation are met.
- The sponsor has a legal responsibility to notify both the local regulatory authority and other regulatory agencies about the safety of a study intervention under clinical investigation. The sponsor will comply with country-specific regulatory requirements relating to safety reporting to the regulatory authority, Institutional Review Boards (IRB)/Independent Ethics Committees (IEC), and investigators.
- An investigator who receives an investigator safety report describing an SAE or other specific safety information (e.g., summary or listing of SAEs) from the sponsor will review and then file it along with the Investigator's Brochure and will notify the IRB/IEC, if appropriate according to local requirements.
- For all studies except those using medical devices, investigator safety reports must be prepared for suspected unexpected serious adverse reactions (SUSAR) according to local regulatory requirements and sponsor policy and forwarded to investigators as necessary.

